5.2. Data Analysis

Similar analyses to those for Aim 2a (see Section 4) will be performed. GLMMs will be used with the indemnity link function for these continuous variables. The intervention effect will be summarized as the mean difference between eSyM+ and eSyM- and reported with a corresponding 95% confidence interval and p-value.

5.3. Power Considerations

Our general approach is to determine the magnitude of difference detectable at a given sample size. Because we have insufficient preliminary information about the magnitude of the ICCs or standard deviations (SD) for our outcomes, we will consider a broad range.

For MO, assuming the average duration of chemotherapy is 180 days in the eSyM- group, the range of detectable between group differences is shown in **Table 11A**. Based on these very

conservative estimates, we have more than 80% power to detect a 16% increase in chemotherapy duration, which corresponds to nearly 1 month.

For Surg, we assume that the average duration from surgery to adjuvant chemotherapy start date (censored at 6 months) is 56 days (8 weeks) in the eSyM- group. With 1212 patients (see **Table 10**), and conservative parameter estimates, we have >80% power to detect a 25% increase in the interval between surgery and starting adjuvant therapy. This corresponds to 14 days, a difference that is both plausible and meaningful, see **Table 11B**.

Table 11: Power considerations for the outcomes of Aim 2b

A: MO 3024 patients (1512 per group)

Detectable effect size with 80% power	Assumed ICC	Assumed standard deviation [Day]	Difference in time to discontinuation	Corresponding ratio in the eSyM- group
0.138	0.01% (Very low)	202 (conservative)	28 days	1.16
		152	21 days	1.12
		101	14 days	1.08
0.170	1%	165 (conservative)	28 days	1.16
		124	21 days	1.12
		82	14 days	1.08
0.174	5% (conservative)	161 (conservative)	28 days	1.16
		120	21 days	1.12
		80	14 days	1.08

B: Surg 1212 patients (606 per group)

Detectable effect size with 80% power	Assumed ICC	Assumed standard deviation	Difference in time to adjuvant chemo	Corresponding ratio in eSyM- group
0.217	0.01% (Very low)	65 (conservative)	14 days	1.25
		32	7 days	1.13
0.256	1%	55 (conservative)	14 days	1.25
		27	7 days	1.13
0.271	5% (conservative)	52 (conservative)	14 days	1.25
		26	7 days	1.13

6. Analysis for Aim 2c: Patients' outcomes, indicated by levels of self-efficacy and symptom burden

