3.1. Randomization

This SW-RCT has 6 steps (figure below), and we randomize 6 sites (**Table 2**) to each of these steps. To ensure that two sites with the same region were not assigned to the same rollout step group (medical oncology live before surgery or surgery live before medical oncology), we employed a stratified randomization by region. As a result, each of the two groups has a site from each of the three regions (Northern, Southern, and Metropolitan). The stepped wedge design includes seven time-periods, including a run-in period (Figure).

Figure: SIMPRO Stepped-Wedge Randomization Schema

Abbreviations: BAPT=Baptist, WVU=West Virginia University, MMC=Maine Medical Center, DHMC=Dartmouth Hitchcock Medical Center, LCI=Lifespan Cancer Institute, DFCI=Dana-Farber Cancer Institute, SIMPRO=Symptom Management Implementation of Patient Reported Outcomes in Oncology

Sequence	Group	Site	eSyM version	Period 1	Period 2	Period 3	Period 4	Period 5	Period 6	Period 7
				Mar '19 - Aug '19	Sep '19 - Feb '20	Mar '20 - Aug '20	Sep '20 - Feb '21	Mar '21 - Aug '21	Sep '21 - Feb '22	Mar '22 - Aug '22
Med Onc live Before Surgery	Southern	BAPT	Med	Pre-live	Live					
			Surg	Pre-live						Live
	Northern	MMC	Med	Pre-live		Live				
			Surg	Pre-live					Live	
	Metrop-olitan	DFCI	Med	Pre-live			Live			
			Surg	Pre-live				Live		
Surgery live Before Med Onc	Metrop-olitan	LCI	Med	Pre-live				Live		
			Surg	Pre-live			Live			
	Northern	DHMC	Med	Pre-live				Live		
			Surg	Pre-live		Live				
	Southern	WVU	Med	Pre-live					Live	
			Surg	Pre-live	Live					

Note: The timing of medical and surgical rollouts is not the same at each site in this SW-RCT. The timing of medical and surgical rollouts was determined so that the number of subjects on the intervention and control would be the same in each site, when medical and surgical cohorts were combined.

Table 2: Six participating sites and Region

Site	Region
WVU	Southern
BAPT	
DHMC	Northern
MMC	
DFCI	Metropolitan
LCI	

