3.3. Number of Subjects

Considering the 2016 tumor registry-reported analytic case volume at each study site for thoracic, GI and Gyn cancers, 12 patients per month per site for each of surgical and medical oncology is a highly conservative estimate of accrual. With 6 sites, assuming equal cluster size, 432 patients will be enrolled both for each period and for each cohort. Thus, a minimum of 6048 patients are expected to be enrolled to the SW-CRT. (Table 3) We will not have a cap for the number of participants for each site. Thus, the number of participants at the end of the study will be different from site to site.

Table 3: Conservative estimates of the accrual numbers for the SW-CRT

Site	MO/ Surg	Period 1 (Run-in)	Period 2	Period 3	Period 4	Period 5	Period 6	Period 7	Total
BAPT	MO	72	72	72	72	72	72	72	504
	Surg	72	72	72	72	72	72	72	504
MMC	MO	72	72	72	72	72	72	72	504
	Surg	72	72	72	72	72	72	72	504
DFCI	MO	72	72	72	72	72	72	72	504
	Surg	72	72	72	72	72	72	72	504
LCI	MO	72	72	72	72	72	72	72	504
	Surg	72	72	72	72	72	72	72	504
DHMC	MO	72	72	72	72	72	72	72	504
	Surg	72	72	72	72	72	72	72	504
WVU	MO	72	72	72	72	72	72	72	504
	Surg	72	72	72	72	72	72	72	504
Total	MO	432	432	432	432	432	432	432	6048
	Surg	432	432	432	432	432	432	432	

Notes:

- The length of each period is 6 months. The run-in period will be at least 6 months, and it will be adjusted so that the total number of eligible episodes under the control condition can be identical to that under the intervention condition.
- The cells colored by blue or grey indicate the periods where the intervention is rolled out in that hospital.

A subset of eSyM+ patients will be asked to complete a research questionnaire called the “SASS Questionnaire (eSyM+ version)” asking about their Self-efficacy, Attainment of information needs, Symptom burden, and Satisfaction with care.

Table 4: SASS Questionnaire accrual numbers (Survey Cohort)							
Site	Surgery			Medical Oncology			Totals
	eSyM- Version	eSyM+ Version	eSyM+ Non-Responder Version	eSyM- Version	eSyM+ Version	eSyM+ Non-Responder Version	
Site 1	75	75	15	75	75	15	330
Site 2	75	75	15	75	75	15	330
Site 3	75	75	15	75	75	15	330
Site 4	75	75	15	75	75	15	330
Site 5	75	75	15	75	75	15	330
Site 6	75	75	15	75	75	15	330
Totals	450	450	90	450	450	90	1,980

eSyM+ : Intervention condition
eSyM- : Control condition

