4.4. Multilevel Generalized Linear Regression Analysis

The primary analysis for the outcomes in Aim 2 (Table 5) will be performed via multilevel generalized linear regression models (or generalized linear mixed-effects model; GLMM).⁹ The null hypothesis for the statistical test is no intervention effect on the outcome, which indicates that the regression coefficient for the intervention indicator variable is zero. The intervention effect will be summarized in both absolute and relative terms (CONSORT Checklist Item 17b).⁷

Followings are specifications of the GLMM for the primary and secondary analyses.

- Link function
 - For binary outcomes, the logit-link will be used.
 - For count outcomes, the log-link will be used, and the follow-up time will be included as the offset in the model. (Poisson regression)
 - For time-to-event outcomes, we will use Poisson regression models, where the log-link will be used. The event indicator (1: event, 0: censoring) will be the response variable. Exposure time (i.e., days from the start date of the follow-up to either the date of the event occurrence or the end of follow-up, whichever comes first) will be included as the offset in the model.
- Treatment effect metrics
 - Following the recommendation of the CONSORT guideline,⁷ we will report the treatment effect in both absolute and relative metrics.
 - For binary outcomes, we will report odds ratio (OR) derived from the GLMM with the logit-link. In addition, we will calculate absolute difference (AD), using the resulting GLMM with G-computation. Bootstrap will be used to obtain a standard error for the estimated AD.
 - For count outcomes and time-to-event outcomes, we will report the incidence rate ratio (IRR) derived from the GLMM model. In addition, we will calculate absolute difference in incidence rate (i.e., incidence rate difference;IRD) in a similar way to calculate AD.
- Secular trend
 - Primary: Calendar time of the start date of the follow-up of each episode will be included as a continuous variable with natural cubic spline with 3 knots
 - Secondary: Period in which the trigger event occurs will be included as a categorical variable.
- Site (cluster)

- Since there are only 6 sites in this study, the conventional analysis of including cluster as random-effects is problematic due to this small number.¹⁰
- Primary: The primary analysis includes sites as fixed effects.

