4.7. Power Considerations

We estimate a minimum of 6048 patients will be enrolled. (see Section 3.3 for details). Since some subjects may experience more than one trigger event (see Section 4.2 General Analysis Approach: *Multiple episodes for medical record data*), the study participants will potentially contribute multiple data points. The goal of the power calculation for this study is to confirm that the study has sufficient power to assess the effects of the intervention on the outcomes. Therefore, for the power calculations throughout this SAP, we will conservatively estimate the power, assuming that an individual patient provides only one episode.

The probability that a patient who has a trigger event experiences EDTR within 30 days after the trigger event is estimated to vary between 8% to 15% for the control group, based on the HCUP data, institutional data, and early phase analyses from CMMI's Oncology Care Model for Baptist Memorial, the only Oncology Care Model participant among our 6 sites. We hypothesize that the probability of experiencing EDTR by Day 30 will be 3 to 4% lower in the eSyM+ group.

Table 9 shows the required sample sizes for the study to have 80% power to detect the difference between groups, at two-sided alpha level 0.05, using the SW-RCT design.¹⁴ Analyses of inter-institutional variation in hospitalization rates and ED visit rates from AHRQ's statewide databases indicate that low ICC estimates are appropriate.^{15,16} Furthermore, we expect a low ICC because: 1) the intervention will be deployed using the same technology across sites; 2) we will adjust for variation in baseline risk via GLMMs such that any potential differences in case-mix among sites will be negligible. Given these factors, the conservative estimate of 6048 participants provides adequate power to address the Aim 2a primary outcome.

Note that we used the sample size formula¹⁴ that assumes exchangeable correlations because we originally had planned to include sites as random effects. However, since the number of sites is only 6 in this study, we modified the analysis plan and decided to include sites as fixed effects in the primary analysis. We acknowledge that our original sample size calculation (above) may not be precise due to this, but it should still work as a conservative estimate.

Table 9. Required total sample size with various scenarios for 80% power					
The probability of experiencing EDTR by Day 30		Effect size		N required	

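### SAP 5.3 claims more than 80% power for Aim 2b, but Table 11's conservative SDs are back-solved from the target difference and its effect sizes assume random sites while the analysis uses fixed sites

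*SAP*

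**What the plan says.** SAP 5.3 sets out to find what difference is detectable at the projected minimum sample size (3024 MO patients, 1212 surgical patients), and says that little is known about the ICCs or SDs. It concludes for MO that "we have more than 80% power to detect a 16% increase in chemotherapy duration", and for surgery that "we have >80% power to detect a 25% increase in the interval between surgery and starting adjuvant therapy". These correspond to 28 days on a control mean of 180, and 14 days on a control mean of 56.

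The first column of Table 11 is headed "Detectable effect size with 80% power". It gives 0.138, 0.170 and 0.174 (MO) and 0.217, 0.256 and 0.271 (surgery) at ICCs of 0.01%, 1% and 5%. The SDs labelled conservative beside them are 202, 165 and 161 days (MO) and 65, 55 and 52 days (surgery).

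On the analysis, SAP 5.2 says "Similar analyses to those for Aim 2a (see Section 4) will be performed", and SAP 4.4 says "The primary analysis includes sites as fixed effects". SAP 4.7 acknowledges, for the Aim 2a calculation, that the formula assumed random sites, and asserts that it remains conservative. Section 5.3 carries no such note.

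**The concern.** A conservative SD is an assumption about patients. It should not shrink because the ICC is assumed larger, yet in Table 11 it does, in both cohorts. That pattern suggests the SDs were solved for rather than assumed. If so, the table cannot show power above 80%.

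The second question is whether random-site effect sizes carry over to a fixed-site analysis. In a stepped wedge with a very small ICC, a random-site model recovers much information from comparisons between sites. Fixed site effects discard it. The rows that look best in Table 11 are therefore the ones most exposed.

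At stake is how an inconclusive Aim 2b result is read. A reader told that power exceeded 80% under very conservative inputs would take a null finding as better evidence against a 28- or 14-day effect than it is.

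**Working it through.** **Inputs.** Error rate and design from SAP 4.7: "at two-sided alpha level 0.05, using the SW-RCT design". It is not restated in 5.3 and is carried over. Layout from SAP 3.1: "The stepped wedge design includes seven time-periods, including a run-in period", six sites, taken as one site crossing per step. Accrual from SAP 3.3: "12 patients per month per site for each of surgical and medical oncology", so m = 12 × 6 = 72 MO patients per site-period. Surgery from Table 10: 202 per site over 7 periods, m = 28.86. Multiplier for 80% power: 1.960 + 0.842 = 2.802.

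**Step 1: reproduce Table 11 (random sites).** Hussey–Hughes variance, with σ² = SD²(1 − ICC)/m and τ² = SD² × ICC:

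Var = Iσ²(σ² + Tτ²) / [(IU − W)σ² + (U² + ITU − TW − IV)τ²]

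Here I = 6, T = 7, U = 21, W = 91, V = 91, so IU − W = 35 and the last bracket is 441 + 882 − 637 − 546 = 140. Detectable effect = 2.802 × √Var at SD = 1:

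| ICC | MO, table | MO, recomputed | Surgery, table | Surgery, recomputed |
|---|---|---|---|---|
| 0.01% | 0.138 | 0.138 | 0.217 | 0.217 |
| 1% | 0.170 | 0.170 | 0.256 | 0.255 |
| 5% | 0.174 | 0.174 | 0.271 | 0.270 |

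The printed effect sizes are the random-site ones.

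**Step 2: where the SDs come from.** 28/0.138 = 203, 28/0.170 = 165, 28/0.174 = 161; 14/0.217 = 65, 14/0.256 = 55, 14/0.271 = 52. All six match Table 11 to within rounding. Each row is therefore a restatement of 80% power.

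**Step 3: is the largest SD possible?** A variable confined to 0–365 days with mean 180 has variance at most 180 × (365 − 180) = 33,300, so SD ≤ 182.5. An MO SD of 202 cannot occur under the truncation in SAP 5.1. Surgery at 65 is feasible: over about 183 days with mean 56, the bound is √(56 × 127) = 84.

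**Step 4: fixed sites.** Letting τ² dominate in the formula gives Var = IT/140 × σ² = (42/140)σ² = 0.3σ². Categorical, linear or cubic time gives the same value in this balanced layout.

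- MO: 2.802 × √(0.3/72) = 0.181.
- Surgery: 2.802 × √(0.3/28.86) = 0.286.

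If the SD is read as a total SD with ICC 5%, multiply by √0.95: 0.176 and 0.278. All of these exceed every entry in Table 11 for the same cohort.

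Power = Φ(difference/SE − 1.96). Example: surgery, SD 65, SE = 65 × √(0.3/28.86) = 6.63; 14/6.63 − 1.96 = 0.15; power 56%. Ranges run from SD as residual to SD as total with ICC 5%.

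| Cohort, target | SD | Power, 7 periods | Detectable days |
|---|---|---|---|
| MO, 28 days | 182.5 | 66–68% | 32–33 |
| | 165 | 75–77% | 29–30 |
| | 161 | 77–79% | 28–29 |
| Surgery, 14 days | 65 | 56–58% | 18–18.6 |
| | 55 | 70–73% | 15–16 |
| | 52 | 75–77% | 14.5–15 |

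Power reaches 80% when the MO SD is at most 28/0.181 = 155 (81% at the table's SD of 152), and when the surgical SD is at most 14/0.286 = 49.

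**Step 5: add Period 8 (SAP 3.6) at the same accrual rate.** N becomes 3024 × 8/7 = 3456 and 1212 × 8/7 = 1385. With T = 8, U = 27, W = 127, V = 139, the bracket is 729 + 1296 − 1016 − 834 = 175 and Var = (48/175)σ² = 0.274σ². Detectable effects are 0.173 (MO) and 0.273 (surgery).

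- ICC 5% row: 80–82% (MO, SD 161) and 79–81% (surgery, SD 52).
- ICC 1% row: MO SD 165 is borderline (0.173 × 165 = 28.5 days, 79–81%); surgery SD 55 is short (0.273 × 55 = 15.0 days, 74–76%).
- Largest feasible SDs: MO 182.5 gives 0.173 × 182.5 = 31.6 days, 70–72%; surgery 65 gives 60–62%.

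**The case against.** The case for leaving the section alone has real content.

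- Section 5.3 says openly that it is finding detectable differences because SD and ICC are unknown. Back-solving an SD to show what would be detectable is legitimate. That stands. What does not follow is calling the solved values conservative, or claiming power above the 80% used to solve for them.
- On the row where SD and ICC are both labelled conservative (ICC 5%; SD 161 or 52), the fixed-site shortfall is only about 1–5 points with seven periods and largely disappears with Period 8. This stands and limits the size of the point.
- The sample sizes are projected minimums. With N doubled and fixed sites, power is 92% at MO SD 182.5 and 85% at surgical SD 65. Smaller SDs in the table also give ample power for the same targets: MO SD 120 gives 95%.
- SAP 4.7 discloses the change from random to fixed sites. But it does so for Aim 2a, and its reassurance runs the wrong way for Aim 2b: fixed sites need a larger effect at all three ICCs.
- Aim 2b is not primary, and SAP 5.2 requires confidence intervals, which limits over-reading of a null result.

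A reader might go further and infer that power is only about 57–61% under the SAP's own conservative values. The documents do not support that. For MO, the 57% needs SD 202 with fixed sites, and the 61% needs SD 202 with random sites at ICC 5%. These are two different models. In both, the SD comes from the row with very low ICC, and 202 is an impossible value.

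**Conclusion.** The point holds as a misstatement of power for a secondary aim. Table 11's conservative SDs are outputs of the target difference. The wording of more than 80% has no support in the table, and the effect sizes belong to a model the analysis no longer uses. With fixed sites the detectable effect is about 0.18 (MO) and 0.28–0.29 (surgery) whatever the ICC, so 0.138 and 0.217 are unattainable at the stated N.

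No SD labelled conservative reaches 80% with seven periods. Including the feasible MO maximum of 182.5, power runs from 66% to 79% for MO and from 56% to 77% for surgery. With Period 8, ICC 5% is the only row where both cohorts return to about 80%.

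This rests on equal accrual at the projected minimum, one site crossing per step, one episode per patient, two-sided alpha 0.05 and no gain from covariate adjustment. It does not show that Aim 2b will be underpowered in fact: accrual above the minimum, or an MO SD of about 152 or less, gives at least 80%. The surgical target worded as an increase is a separate slip against the hypothesis in 5.1 of earlier initiation; it does not alter two-sided power.

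**What to change.** In SAP 5.3:

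1. Recompute Table 11 under the fixed-site model for the current number of periods, and say so.
2. Apply one feasible SD range to every row, with MO capped at about 182 days.
3. Report the resulting detectable differences. With seven periods these are about 32–33 days at MO SD 182.5 and 18–18.6 days at surgical SD 65. With eight periods they are about 31–32 and 17–18 days.
4. Replace the claims of more than 80% power and of very conservative estimates with the recomputed power.
5. State the surgical target as a decrease, to match 5.1.

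The cost is wording and a short recalculation. No patients are added and the analysis does not change. The downside is that the published figures become less favourable.

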6.1. Outcomes and summary measures

The outcomes investigated in Aim 2c of the SIMPRO study are classified into four groups, depending on the data source and data collection schedule. **Table 12** shows the details of the groups and the disposition of each outcome in Aim 2c.

Table 12: Outcomes in Aim 2c		
Type	Outcome Type in the SIMPRO study	Example outcomes in Aim 2c
1	Measured at one single time point only either in post-intervention (the intervention condition) or in pre-intervention (the control condition) for all or selected subjects (patients or providers)	eSyM decline (1 st time)
2	Measured at multiple time points (periodically) only in post-intervention period for all or selected subjects (patients or providers)	eSyM logins per patient per month
		Frequency of patient eSyM reports with severe symptoms
3	Measured from selected subjects (patients or providers) at a single time point, which could be during the pre-intervention period or the post-intervention period. For some subjects, data may be collected at both periods.	PROMIS items (self-efficacy for managing symptoms, pain interference, fatigue, and physical function)
4	Measured periodically through the SW-CRT design from all eligible subjects.	MyChart activation (binary outcome)
		MyChart logins per patient per month

6.2. Data Analysis

Analysis of Outcomes classified as Type 1:

- For descriptive purposes, we will estimate crude means for continuous outcomes and crude proportions for dichotomous outcomes and calculate corresponding 95% confidence intervals by site. The coefficient of variation is calculated using the site-specific point estimates.
- Next, we estimate the overall mean (or proportion). To this end, a weighted mean and corresponding 95% confidence interval will be calculated using the site-specific point estimates and their standard error estimates, using the inverse of the site-specific variance estimates for the weights.
- In addition, generalized linear models (GLMs) will be used to investigate factors associated with the outcome. In the GLMs, we will account for site variability by treating "site" as a fixed effect. For modeling continuous outcomes, we will use the identity link function. For dichotomous outcomes, the logit link function is used.

Analysis of Outcomes classified as Type 2:

- We will calculate the site-period-specific means (or proportions), adjusted for the factors potentially associated with the outcome. We will calculate the coefficient of variations across sites and also across periods, respectively.
- To this end, we will use generalized linear mixed-effects models (GLMMs). In GLMMs, we will account for site variability by treating "site" as a fixed-effect, secular trend by treating "period" as a fixed-effect, and within-subject variability by treating "subject" as random-effects. For modeling continuous outcomes, we will employ the identity link function. For

dichotomous outcomes, the logit link function will be utilized. G-computation will be used to derive the site-period-specific means (or proportions).

- We will also calculate the site-specific, period-specific, and overall means (or proportions) and corresponding 0.95 confidence interval by taking a weighted average of the site-period-specific mean values (or proportions) obtained through GLMMs. The reciprocal of the variance-covariance matrices of the site-period-specific mean values (or proportions) will be used as the weight.

Analysis of Outcomes classified as Type 3:

- For descriptive purposes, we will estimate crude means for continuous outcomes and proportions for dichotomous outcomes and calculate corresponding 95% confidence intervals by intervention group (eSyM+ vs. eSyM-) and site.
- Using these results, the difference between the intervention condition (eSyM+) and the control condition (eSyM-) along with a corresponding 95% confidence interval will be calculated for each site. In addition, using the point estimates from the six sites, we will calculate the coefficient of variation of the difference between conditions.
- We will then estimate the overall between-conditions difference integrating the site-specific differences. Specifically, a weighted average and corresponding 95% confidence interval will be calculated, using the site-specific point estimates their standard error estimates, where the reciprocal of the site-specific variance estimates will be used for the weights.
- In addition, generalized linear models (GLMs) will be used to investigate factors associated with the outcome. In the GLMs, we will include the intervention indicator, “site” and other factors (i.e., age (at cancer diagnosis for medical oncology patients and at index surgery for surgical patients), sex, employment status, education, ability to pay bills, and technology confidence) as independent variables. For modeling continuous outcomes, we will employ the identity link function. For dichotomous outcomes, the logit link function will be utilized. Note that, when more appropriate (where some subjects have data from both pre- and post-intervention periods), we will use GLMMs by treating “subject” as random-effects instead of GLMs for some outcomes.

Analysis of Outcomes classified as Type 4:

- We will estimate the intervention effect on each outcome.
- To this end, analyses similar to those for Aim 2a (see Section 4) will be conducted. GLMMs will be used with the identity link function for continuous outcomes and with the logit link function for dichotomous outcomes. The intervention effect will be summarized as the mean difference and odds ratio for continuous outcomes and dichotomous outcomes, respectively, and reported with a corresponding 95% confidence interval and p-value.

Interpretation of the PROMIS scores: Note that Yost and Cella have reported minimally important difference (MID) ranges for five PROMIS domains including fatigue, pain, depression, anxiety, and physical functioning^{17,18} Cella recommends using 0.5 SD as the MID for PROMIS scales^{19,20}

Approach to missing data for PROMIS scores: Because a random missing mechanism assumption is not verifiable, we will use several methods to handle missing observations. Specifically, we will perform: (1) mean value; (2) worst-case; (3) best-case; and, (4) multiple imputations.¹³

7. Analysis for Aim 2d: Patients' satisfaction with their cancer care

